Data collection will occur outside hookah cafés in the Atlanta, GA metro area. Atlanta was chosen as the study site because Georgia's weak smoke-free air law allows smoking in bars and restaurants, including hookah cafés. There are over 100 hookah cafés in the Atlanta metropolitan area and Atlanta is home to 57 colleges and universities. The number of cafés and young adults, and the weak smoke-free air laws make Atlanta the ideal location for this study. We will partner with one pilot café and up to 31 additional cafés to allow study activities, including collecting data with customers before café entry and after café exit, and display of study-produced health warnings about hookah smoking during the times when data collection is occurring. Participants will complete data collection outside of the café at two time points, before entry into the café and after exit from the café.

Subject Selection Criteria

Participants will be those planning to enter a hookah café where the study is being conducted. We aim to have 15 participants complete Time 1 (before café entry) and Time 2 (after café exit) data collection at each café for each arm. In order to account for attrition between time points, we will enroll up to 30 participants at each café during each data collection period. We will schedule data collection periods for when the café is most busy, based on information provided by the café manager or owner.

Inclusion Criteria

- Planning to enter the hookah café where study is being conducted
- Age 18 or older
- English speakers
- Planning to smoke hookah inside
- Planning not to smoke cigarettes, cigars, cigarillos, or marijuana while at the hookah café
- Had not previously entered the café earlier in the day on the same day/night as data collection
- Has not been approached to participate in the study at another café or another day/night at the current café
- Are not employees of the business
- Have capacity to participate as determined by the staff member conducting eligibility screening

Exclusion Criteria

- Not planning to enter the hookah café where the study is being conducted
- Age 17 or under
- Non-English speakers
- Not planning to smoke hookah in the café
- Planning to smoke cigarettes, cigars, or marijuana while at the hookah café
- Are employees of the business
- Has not been approached to participate in the study previously
- Had previously entered the café on the same day/night as data collection

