Data collectors will also make a determination, based on their interaction with the participant, of the participant's capacity to participate in the study. If they determine that the person does not have capacity, they will mark this on the Eligibility Form and the participant will be Not Eligible. If they determine that the person does have capacity, they will mark the participant such on the Eligibility Form and will continue with the Consent process. Determination of capacity to participate will be based on whether people can adequately answer the eligibility screening questions. Eligible participants will be read the consent information by a data collector prior to enrollment and provide verbal consent. A printed consent document will be available for participants if they ask to see it.

After completing the consent process, participants will be given a wristband with their participant ID. Then, they will complete a brief survey about their hookah use behaviors, demographics, and recent use of other combustible products. They will enter their email into a Qualtrics link managed by Ewald & Wasserman to receive their first (\$25) electronic gift card; this is not stored with study data, although it is linked to PID. Next, participants will provide up to two samples of expired carbon monoxide (eCO) by blowing into a carbon monoxide (CO) monitor. This non-invasive process involves taking a deep breath, holding it for 15 seconds, and then exhaling into a sterile tube until the lungs are completely empty. Expired CO is a well-established measure of tobacco smoke exposure. Participants will then be able to enter the café as planned. All participants will be asked to return to the data collectors after exiting the café to complete the follow-up measures. If the data collection period is scheduled to end before the café closes, data collectors will instruct the participants to come outside for Time 2 measures before the data collection period will end. Upon exiting the café, participants will complete a similar brief survey, provide their email again for their second (\$50) compensation, and provide up to two new samples of eCO, using the same procedure as described above. Participants will be debriefed on the purpose of the study and the CO measure. The debrief form will also have resources for more information about CO and health harms of hookah smoking, and contact information for the study PI, the Wake Forest IRB, and E&W for assistance with compensation.

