The participant incentives are not intended to be an enticement to smoke hookah within the café, but rather as compensation for time needed to complete the surveys and eCO monitoring, which we anticipate will take up to 20 minutes at each time point. Participants will only be eligible if they indicate they are planning to smoke hookah in the café. We will not recruit people to come to the café, but rather recruit café customers to participants in the study. Participants will be instructed to behave as they normally would in the café. The incentive will not be able to be used in the café.

Figure 1. Table Sign

Pilot/Soft Launch

We will conduct a pilot/soft launch with a single hookah café to assess feasibility of the protocol and to make changes, if required, before conducting the full trial. Any changes to protocol and/or measures will be submitted as amendments before conducting the remainder of the trial. If no changes are made as a result of the soft launch, this café will be included in the final study sample. If significant changes are made as a result of the soft launch, we will conduct the study with up to 25 additional cafés and the data from the soft launch café will not be included in the final dataset. We will implement both text-only and pictorial warnings on different nights at the pilot café to fully test the two versions of the intervention signs, in addition to the control arm.

Outcome Measure(s)

Primary Outcome

Change in Expired Carbon Monoxide from baseline to follow-up. We will use eCO, an objective, biological marker of waterpipe tobacco consumption. There is a linear relationship between waterpipe tobacco smoking intensity and carboxyhemoglobin concentration, and eCO is strongly correlated with several topography measures of waterpipe smoking. Carbon monoxide has a half-life of 3-4 hours and is influenced by other forms of combustible tobacco; therefore, the primary outcome will be the change in eCO from before entry to after café exit, known as eCO boost. We will also record the percentage of carboxyhemoglobin concentration measured by the CO monitor.

Secondary Outcome(s)

None

Other Outcomes

Behavioral intentions. Participants will be asked at Time 2 three items assessing their expected hookah smoking within the next month. Items will be averaged to create a composite score of intent to continue the behavior within the next month.

1. How interested are you in smoking tobacco in a hookah in the next month?

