Warning recognition (Intervention Arms Only). Participants will be asked to select the warning(s) that they saw at the café from a selection of the four possible warnings for their study arm. For each warning message that they report having seen, they will be asked to select where they saw the warning from a list of possible locations.

Social interactions. For each warning selected in the Warning Recognition section, participants will be asked if they discussed the warning with others. If they answer positively, they will be given a list of topics to choose from to describe what they talked about, including a free-text option.

Perceived influence of warning on smoking behavior. Participants will be asked whether they changed their smoking behavior as a result of the warning(s) they saw (as reported in the Warning Recognition section). They will be asked to report whether they smoked more, less, or the same amount as they usually do. These items will be asked for each warning the participant reports seeing.

Time spent in the café. Duration of time in café will be calculated from the time of completion of eCO measurement at Time 1 to start of survey at Time 2. Additionally, we will utilize a subjective measure of time spent in the café: Compared to what you planned, how long did you stay at the café/lounge/bar? (Longer, shorter, about the same).

Analytical Plan

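### When a data collection period ends before the café closes, the schedule sets Time 2 for anyone still inside, and the plan does not record or analyse these stays as cut short

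*Combined protocol and SAP*

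**What the plan says.** Time 2 has two triggers in the protocol's Data Collection section. The default is the participant's own departure: "All participants will be asked to return to the data collectors after exiting the café to complete the follow-up measures". The exception is conditional: "If the data collection period is scheduled to end before the café closes", the collectors "data collectors will instruct the participants to come outside for Time 2 measures before the data collection period will end". The same section says: "Participants will be instructed to behave as they normally would in the café".

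Under Primary Outcome, "the primary outcome will be the change in eCO from before entry to after café exit, known as eCO boost". Under Other Outcomes, time in café runs "from the time of completion of eCO measurement at Time 1 to start of survey at Time 2", and a separate item asks whether the stay was longer, shorter or about the same as planned.

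Period times are agreed with each café (Data Collection). No section fixes the length of a period, matches it between a café's control and intervention periods, sets a last enrolment time, or asks for prompted exits to be recorded. The model in the Analytical Plan has a fixed arm effect, random café and café-arm effects, and adjustment for sociodemographics and baseline tobacco use. Nothing in it deals with sessions ended by the schedule.

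**The concern.** The eCO boost is meant to capture how much a person smoked during a visit. For someone brought out by the schedule, it captures smoking up to a time that staff and café agreed beforehand. The duration variable treats that time as the length of the visit, although the person might have stayed longer or might go back in. A reply of shorter than planned would then reflect the schedule and not the warning. The same holds for a report of smoking less than usual.

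Two consequences follow for the comparison. First, if warnings work by shortening stays or reducing total smoking, cutting sessions removes part of the difference that the trial is looking for. Applying the rule in both arms does not prevent this, because shorter stays under warnings would leave more control participants inside at the cut-off. Second, each café's arms run in separate periods. If one period ends earlier in the evening than the other, the share of cut sessions can differ by arm for reasons unrelated to the warning, and that can push the contrast either way.

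Without a record of exit type, none of this can be reliably identified afterwards.

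**Working it through.** **1. The plan's own figure.** Inputs from the Analytical Plan: k = 20 cafés, m = 15 per arm, SD = 30 ppm, h = r/2, power 80%. Two-sided alpha of 0.05 is assumed, since none is stated.

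SE = SD × √(2[1 + (m − 1)r − mh]/(km)); detectable difference = (1.960 + 0.842) × SE.

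- r = 0.10, h = 0.05: bracket = 1 + 1.40 − 0.75 = 1.65; SE = 30 × √(3.30/300) = 3.146; difference = 8.815 ppm (stated 8.81).
- r = 0.30, h = 0.15: bracket = 1 + 4.20 − 2.25 = 2.95; SE = 30 × √(5.90/300) = 4.207; difference = 11.787 ppm (stated 11.78).

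Both reproduce.

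**2. Equal truncation in both arms (illustration).** Let f be the share of stays cut and g the part of the arm difference that those people keep. The observed difference is multiplied by 1 − f(1 − g). Neither f nor g is in the documents. Power at the stated detectable difference, SD held at 30, is the same for both values of r:

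| f | g | Multiplier | Power | True difference needed for 80% power, r = 0.10 |
|---|---|---|---|---|
| 0 | – | 1.00 | 80% | 8.81 ppm |
| 10% | 0.5 | 0.95 | 76% | 9.28 ppm |
| 20% | 0.5 | 0.90 | 71% | 9.79 ppm |
| 20% | 0 | 0.80 | 61% | 11.02 ppm |

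**3. The same idea at the protocol's pilot effect.** 26.0 puffs × 0.4 ppm = 10.4 ppm. Power here uses a noncentral t with 19 df, which is more cautious than the plan's normal quantiles.

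- No truncation: 88% (r = 0.10), 65% (r = 0.30).
- 30% cut, each losing one third: 10.4 × (1 − 0.30/3) = 9.36 ppm; 81% and 56%.
- 40% cut, each losing half: 10.4 × (1 − 0.40 × 0.5) = 8.32 ppm; 71% and 47%.

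These figures hold the SD at 30. If boosts shrink in proportion around the cited mean of 51.7 ppm, the second scenario has variance (0.7 + 0.3 × 4/9)(30² + 51.7²) − (0.9 × 51.7)² = 812, so SD = 28.5. Power is then 84% and 60%, a smaller loss.

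**4. Unequal truncation between arms (illustration).** Bias = difference between arms in share cut × share of boost lost × 51.7 ppm.

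- 10 points, 25% lost: 0.10 × 0.25 × 51.7 = 1.3 ppm.
- 10 points, 50% lost: 2.6 ppm.
- 20 points, 50% lost: 5.2 ppm.

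More cutting in the control arm shrinks an apparent reduction in boost; more cutting in the intervention arm inflates it. For scale, the detectable difference is 8.81 ppm at r = 0.10.

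**5. Duration.** No arithmetic is needed. The rule stops the clock at the start of the Time 2 survey whatever brought the person out, so a prompted exit gives only a lower limit on the stay but is stored as its length.

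**The case against.** A reader might infer that the rule contradicts the primary outcome definition. It does not: people come outside and are measured outside, so the change is still from before entry to after exit. What is left is a tension with the instruction to behave as normal, and an event that the analysis does not address.

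The wording need not mean that staff go in and fetch people. It may be notice given at Time 1 of when staff leave. That weakens any picture of interrupted sessions, but the schedule would still set the end point, and notice may itself change pace or length of stay. The rule also has a purpose: without it, anyone inside when staff leave would have no Time 2 at all. Attrition is foreseen: "In order to account for attrition between time points, we will enroll up to 30 participants at each café".

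A reader might also infer that those lost are the longest stayers, or that the bias must be toward zero. The documents establish neither. If warnings act early in a session, cutting its end removes little. The power figures rest on assumed shares, and steps 2 and 3 apply equal truncation to both arms, so they do not measure harm from unequal truncation.

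The items on stay against plan and on reasons for smoking less capture some of this. They cannot reliably identify a prompted exit, and are themselves affected by one. The Time 2 Survey, eCO Form and Interviewer Scripts are listed in the Appendix but not reproduced, so a field or a last enrolment time may exist there. If so, the remaining gap is in the analysis and in matching the windows.

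**Conclusion.** The point holds as a cheap improvement. For prompted exits, the duration rule stores a censored stay as a completed one whenever the rule applies. For the eCO boost, dilution is possible if warnings act through length of stay or total smoking, and bias in either direction is possible if windows differ between a café's two periods. Neither is certain.

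The size cannot be stated from the documents. It depends on how many periods end before closing, how many people are then still inside, and how much of their session remains. If every period runs to closing, the effect is zero. The illustrations show only that modest shares would matter in a design powered at 80% for its stated difference. They are not evidence of an actual loss of power.

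**What to change.** 1. Use the same start and end clock times for a café's control and intervention periods.
2. At Time 2, record whether the exit was prompted by the end of the period and whether the person plans to go back in.
3. Treat the duration of prompted exits as right-censored, in a model that accepts censoring.
4. Add a sensitivity analysis of eCO boost limited to participants whose Time 1 clock time left room for a full stay. Fix the threshold before any comparison by arm; soft-launch stay times can inform it, though they come from one café. This restriction is set before exposure to the warning. Do not adjust for time in café instead, since duration follows exposure and may carry part of the effect.
5. Report Time 2 completion and prompted exits by arm.

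A last enrolment time is optional, because it may cost completions toward the target of 15 per café and arm.

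The cost is one extra field, a scheduling constraint and one extra model. The restricted analysis will be less precise and will describe earlier arrivals only.

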the partner café. However, each café will only have one warning displayed on its premises for the duration of its participation in the intervention arm.

Objective(s)

1. To determine the effect of warnings on hookah smoking behavior, measured with an objective biomarker of consumption (expired carbon monoxide), and behavioral antecedents.

Roles

Wake Forest Baptist Health

Wake Forest's role in this study will be to develop the protocol and data collection instruments, create the study stimuli, program all online data collection tools, train data collectors hired by Ewald & Wasserman, monitor data collection, conduct all analyses, and lead dissemination of results.

University of North Carolina at Chapel Hill

[name] will assist in developing data collection instruments and interpreting the results of analyses on final data.

Boston University

[name] will assist in developing data collection instruments and interpreting the results of analyses on final data.

Ewald & Wasserman Research Consultants, L32

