Ewald & Wasserman (E&W) will conduct the Aim 3 cluster randomized crossover trial at up to 32 hookah cafés (1 pilot and 31 trial cafés) in Atlanta, GA. This trial will be conducted entirely in the field at the participating cafés. Hookah cafés will be recruited to partner with the research team, which involves allowing participants to be recruited and data collection to occur outside the café prior to café entry and after café exit on at least two data collection periods (across the two trial arms). Cafés must also agree to allow the research team to post health warnings about hookah smoking in the cafés on some of the days of data collection. E&W will be responsible for the recruitment of hookah cafés, hiring of field staff, training of field staff on data collection procedures (in conjunction with the Wake Forest study team), and implementing all data collection procedures. Data collection will involve field research at the hookah cafés. Field staff will approach potential participants before they enter the café to assess interest in the study and eligibility. For those eligible, field staff will complete the consenting process, administer a brief survey on tablet computers, collect expired carbon monoxide breath measurements, and distribute incentives at two time points: before participants enter the café and after they exit. Additionally, field staff will debrief participants at the end of the study. E&W will also be responsible for all participant payments. Finally, E&W will be responsible for printing, implementing, and removing the warning signs at waterpipe cafés.

Methods and Measures

Design

The design of the study is a cluster randomized crossover trial, where the hookah café is the cluster and randomization is at the cluster level. Each hookah café will serve as its own control and will be used for data collection for both study arms: (1) intervention, and (2) control. Each café will start in the no warning control arm to avoid the potential for contamination, since customers may visit the same café on multiple days. In the intervention arm, cafés will display one of four text warnings. In the intervention arm, warning messages will be displayed at various agreed-upon locations in the café, such as on hookah pipes, tables, countertops, walls, and menus. The goal is to maximize the potential for customers to be exposed to warnings.

Setting

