The sample size will allow us to detect meaningful differences in the eCO boost between study arms. We estimate the minimum difference in eCO boost detectable between the two arms (intervention vs control) with 80% power between two periods I using a cluster randomized crossover trial design with a minimum of 20 cafés, each with completed data for 30 café patrons (15 per arm). Sample size is based on formulae from Giraudeau et al. (2018) that takes into account both the intraclass correlation coefficient r (correlation within a café) and the inter-period correlation h induced by the crossover design.¹³ We consider both small and moderate ICCs or $r=0.10$ and $r=0.30$ and a smaller h specified to be half of r as recommended by Donner et al. (2004).¹⁴ A review of the literature¹⁵⁻¹⁸ suggests a standard deviation of $s=30$ parts per million (ppm) for the change in eCO. Based on these assumptions, we will have 80% power to detect differences in eCO boost between two periods of 8.81ppm for a low r and 11.78ppm for a moderate r . In one of the few studies in waterpipe cafés, the mean absolute change in CO was 51.7ppm with a relative boost of 795%.¹⁵ we are more than sufficiently powered to detect differences this large as well as much smaller changes in the range of 8.81ppm to 11.78ppm. We can convert this to number of fewer puffs based on data that a single puff results in a 0.4ppm eCO boost.¹⁹ We will be able to detect a reduction of between 22.0 and 29.4 puffs.²⁰ This is consistent with the reduction in mean puffs (26.0) found in the lab-based pilot study of WTS warnings.²¹

A hierarchical linear modeling (HLM) approach (model C1 in Turner et al. 2007) will be used for the analysis.¹³⁸ In contrast to cluster-level methods, which aggregate data, hierarchical modeling offers more flexibility and allows us to incorporate both café-level and individual-level covariates, as well as the correlation

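### At Time 2 the primary breath sample is listed after the survey and payment step; taking it first on exit would remove a small delay that is probably somewhat longer in the intervention arm

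*Combined protocol and SAP*

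**What the plan says.** For Time 2, the Data Collection section reads "Upon exiting the café, participants will complete a similar brief survey, provide their email again for their second" payment, followed by up to two eCO samples and the debrief. The Roles section also puts the survey ahead of the breath measurement at both time points. Under Other Outcomes, time in the café runs "from the time of completion of eCO measurement at Time 1 to start of survey at Time 2", which fits a survey-first order and leaves the survey-to-breath gap outside that measure.

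The Time 2 survey differs by arm. Other Outcomes has a block labelled "Warning recognition (Intervention Arms Only". For each warning a participant reports having seen, it leads to questions on where it was seen, whether it was discussed, and whether it changed smoking. The introduction states that "each café will only have one warning displayed on its premises", so these follow-on items would normally be asked once, and not at all of someone who recognises no warning.

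The Primary Outcome section says "Carbon monoxide has a half-life of 3-4 hours". Data Collection describes the time needed for surveys and eCO together as something "which we anticipate will take up to 20 minutes at each time point". The model in the Analytical Plan adjusts for sociodemographics and baseline tobacco use, with party size added in secondary analyses. It has no term for the interval from exit to breath, and nothing in the text limits or equalises that interval.

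**The concern.** The primary outcome is meant to capture CO at café exit. Every minute between exit and breath lowers the reading, and the delay has two parts.

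- **Extra delay in the intervention arm.** Being in the intervention arm, and noticing the warning, lengthens the questionnaire that precedes the measurement. If the warning does nothing, this produces a small apparent reduction in its favour.
- **Delay common to both arms.** This shrinks the boost, and with it any true difference.

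When there is a true effect the two parts pull in opposite directions, so the net bias can have either sign. What is at stake is a small, avoidable systematic error in the only primary outcome.

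**Working it through.** **The plan's own detectable difference.** Inputs from the Analytical Plan: k = 20 cafés, m = 15 per arm per café, SD 30 ppm, ICC r = 0.10 or 0.30, inter-period correlation h = r/2, 80% power. Two-sided alpha of 0.05 is assumed because none is stated.

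SE = 30 × √[(2/(m·k)) × (1 + (m−1)r − m·h)]; detectable difference = (1.96 + 0.84) × SE.

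- r = 0.10: the last bracket is 1 + 1.4 − 0.75 = 1.65; SE = 3.15; difference = 8.81 ppm.
- r = 0.30: the last bracket is 1 + 4.2 − 2.25 = 2.95; SE = 4.21; difference = 11.79 ppm.

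The plan states 8.81 and 11.78 ppm, so these standard errors can be used below.

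**Exit level and clearance rate.** The Analytical Plan cites a café study in which "the mean absolute change in CO was 51.7ppm with a relative boost of 795" per cent. Implied baseline = 51.7/7.95 = 6.5 ppm; exit level = 51.7 + 6.5 = 58.2 ppm. Rate of fall = 58.2 × ln 2 / half-life, which is 0.224 ppm/min at 3 h and 0.168 ppm/min at 4 h.

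**No effect of the warning, extra delay d in the intervention arm.** False reduction = 58.2 × (1 − 2^(−d/half-life)). The range of d is an assumption. Puffs use the plan's 0.4 ppm per puff.

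| Extra delay | 4 h half-life | 3 h half-life | Share of 8.81 ppm | Puffs |
|---|---|---|---|---|
| 1 min | 0.17 ppm | 0.22 ppm | 1.9–2.5% | 0.4–0.6 |
| 2 min | 0.34 ppm | 0.45 ppm | 3.8–5.1% | 0.8–1.1 |
| 5 min | 0.83 ppm | 1.11 ppm | 9.5–12.6% | 2.1–2.8 |

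With bias b, two-sided type I error = Φ(−1.96 − b/SE) + 1 − Φ(1.96 − b/SE).

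- b = 0.45 ppm: 5.2% at r = 0.10 and 5.1% at r = 0.30.
- b = 1.11 ppm: 6.4% at r = 0.10 and 5.8% at r = 0.30.

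**Common delay c.** Fraction lost = 1 − 2^(−c/half-life).

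- 10 minutes (assumed): 2.8–3.8%.
- 20 minutes: 5.6–7.4%. This is a ceiling, because the plan's 20 minutes also covers the eCO measurement.

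**Both parts, with a true effect of 8.81 ppm.** The intervention exit level is 58.2 − 8.81 = 49.4 ppm. Observed difference = 58.2 × 2^(−c/half-life) − 49.4 × 2^(−(c+d)/half-life). With c = 10 minutes:

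- d = 1 minute: 8.66–8.70 ppm.
- d = 5 minutes: 9.25–9.38 ppm.
- The two parts cancel at d ≈ 1.8 minutes (about 0.9 if c = 5, about 2.8 if c = 15).

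**Switching the order between a café's two arms.** The differential delay would then be the whole survey time. At 5–15 minutes (assumed) that is 0.83–3.27 ppm.

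**The case against.** The strongest objection is size. With 1–2 extra minutes the bias is 0.17–0.45 ppm against a standard error of 3.15 ppm, and type I error barely moves. The 6.4% figure needs the top of an assumed range, the shorter half-life and the lower ICC all at once, and five extra minutes as an arm average is a lot for a few items in a brief survey. This stands, and it is why the point has low priority.

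Second, clearance is proportional, so a common delay should shrink the spread of exit readings along with the mean difference. This also stands: the claim here is a smaller estimated difference in ppm, not a loss of power.

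Third, the Time 2 steps are a plain list, whereas Time 1 uses sequence words. The Roles section puts incentives after the breath, so the position of the email step is less certain than that of the survey. The Time 2 Survey, eCO Form and Interviewer Scripts are appendix items not shown, and they may fix the order or record breath times. That is a fair limit on certainty, but both sections put the survey before the breath. A time-stamp would allow a sensitivity analysis without removing the delay.

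Fourth, the present order automatically keeps the CO reading from influencing the knowledge, belief and intention items, and one of the four warnings concerns carbon monoxide poisoning. This is a real advantage, which the new order must replace by withholding the reading.

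Finally, sampling first does not remove the time from last puff to exit, or queueing for the monitor. That is correct; time-stamps would document the breath time but not the last puff.

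**Conclusion.** The point holds as a low-priority but worthwhile improvement. The documents list the primary measurement after a survey that contains intervention-only items, and neither the procedures nor the model deals with the resulting interval. With no true effect, the false reduction is about 0.2–1.1 ppm, and under 0.5 ppm if the extra items take only 1–2 minutes. With a true effect the net bias can go either way and is near zero at about 1.8 extra minutes.

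These figures rest on the plan's half-life, on the exit level from the single café study it cites, on treating the whole exit level as clearing at that rate, and on assumed survey times. The extra delay itself is inferred from the survey content; no timings by arm are given. The direction of the differential delay is well supported, but its length is unknown.

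**What to change.** At Time 2, take both eCO samples first, immediately on exit, and time-stamp them; then run the survey and payment steps. Withhold the reading until the debrief. End time in the café at the Time 2 eCO time-stamp, which is still the first step after exit. Leave Time 1 as it is, since eCO is already the last step before entry.

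If data collection is under way, apply the new order only to cafés that have not begun their control period. The plan says "Each café will start in the no warning control arm", so a change between a café's two arms would load the whole survey time onto the control period. On the assumed 5–15 minutes, that biases the result by 0.8–3.3 ppm against the warning, which is larger than the problem being fixed. For cafés already started, keep the existing order and use recorded survey and breath times, where they exist, in a sensitivity analysis.

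The cost is an edit to the protocol and interviewer script, with the same staff, device and number of samples. The two downsides are that staff must keep the reading from participants during the survey, and that the changeover must be made between cafés.
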